11.5	Investigator Responsibility	35
11.6	Statement of Insurance to be Provided to the Study Subjects	36
12	PUBLICATION POLICY	36

[REDACTED]

ABBREVIATIONS AND DEFINITIONS

ABBREVIATIONS

AE	Adverse Event
CFR	Code of Federal Regulations
CRF	Case Report Form and eCRF for Electronic Forms
CRO	Contract Research Organization
D	Diopter
DW	Daily Wear
FDA	U.S. Food & Drug Administration
FRS	Foresight Regulatory Strategies, Inc.
GCP	Good Clinical Practices
HIPAA	Health Insurance Portability and Accountability Act
IB	Clinical Investigator's Brochure
ICD	Informed Consent Document
IDE	Investigational Device Exemption
IRB/IEC	Institutional/Independent Review Board / Independent Ethics Committee
ISO	International Standards Organization
MK	Microbial Keratitis
MPS	Multi-Purpose Disinfection Lens Care System
OHRP	Office for Human Research Protections
OHSR	Office for Human Subjects Research
PHI	Protected Health Information
QA	Quality Assurance
QC	Quality Control
SAE	Serious Adverse Event / Serious Adverse Experience
SCL	Hydrogel Contact Lens
SHCL	Silicone Hydrogel Contact Lens
SOP	Standard Operating Procedure
UADE	Unanticipated Adverse Device Effect
USADE	Unanticipated Serious Adverse Device Effect
VA	Visual Acuity

ABBREVIATIONS AND DEFINITIONS

DEFINITIONS**Principal Investigator: (PI)**

A duly licensed and properly trained individual responsible for the conduct of the clinical study at the study site. If a trial is conducted by a team of individuals at a trial site, the Principal Investigator is the responsible leader of the team. The PI must have the qualification of an Optometrist or Ophthalmologist.

Sub-Investigator: (SI) An individual member of the clinical study team designated and supervised by the principal investigator. The individual is able to perform critical study-related procedures and/or to make important study-related decisions. These properly trained individuals may be study coordinators, residents, research fellows or properly qualified and licensed Optometrists or Ophthalmologists.

Licensed Investigator: For the purpose of this protocol a Licensed Investigator will be an Optometrist or Ophthalmologist who possesses a current license in good standing for the State where he/she is currently practicing and participating in the clinical study.

Investigator: For the purposes of this protocol, an Investigator will be any of the individuals described in the definitions above of Principal Investigator and Sub-Investigator.

Data Collection and Entry: Data collection and entry may be performed by the Principal Investigator or any of the various levels of qualified Sub-Investigators. Only the PI or a professionally licensed Optometrist or Ophthalmologist SI may review the review visit data entered and complete the signature form at the completion of the visit.

Investigational Materials: The materials evaluated in the clinical study will be designated as either the Test or Control material. The Test material will be a new material that has not been previously cleared or determined to be substantially equivalent using the FDA's 510(k) review process. The material designated as the Control will have previously been review by FDA and has received a clearance under the FDA's 510(K) review process.

1 BACKGROUND

Hydrogel Contact Lenses (SCLs) and Silicone Hydrogel Contact Lenses (SHCLs) have been developed and marketed with a number of wear and care modalities to meet a variety of ocular health and convenience needs. These modalities include the periods of lens use and disposal wherein lenses are worn for months, weeks, or one day prior to disposal. Lenses used for more than a single use require the use of accessory lens care systems (multiple or single bottles) for lens cleaning, overnight storage, disinfection and lens rinsing prior to repeated insertion.

The Sponsor has developed a silicone hydrogel contact lens material for use in a recommended one month replacement modality. The material characteristics of this formulation place the material into the FDA Classification for Silicone Hydrogel materials of Group 5. Using this information the study is designed to evaluate the new CooperVision silicone hydrogel contact lens material (Test Lens) to demonstrate substantial equivalence to a material in the same class (Control Lens).

2 STUDY OBJECTIVE

The objective of this evaluation is to provide evidence supporting the claim that the performance of the Test Lens is substantially equivalent to that of the Control Lens when used in a one month recommended replacement, daily wear modality.

Based on previous evaluations of this lens design and material formulation and published information on the performance of other contact lenses marketed for similar uses, and based on the FDA Premarket Notification 510(k) Guidance Document for Daily Wear Contact Lenses (May 1994) this is a non-significant risk study.

3 INVESTIGATIONAL PRODUCTS

Both Invigor A and Invigor B lenses are silicone hydrogel contact lenses. They will be used following a daily wear schedule with a recommended replacement schedule of one month.

3.1 Investigational Lens Names and Descriptions

Both Invigor A and Invigor B silicone hydrogel contact lenses are manufactured by CooperVision, Inc. Each study lens has a non-ionic surface and requires no surface treatment to impart wettability.

Each lens type will be available in the following powers and diameters:

Lens Powers:	-0.50 D to -6.00 D (0.25 D steps) -6.50 D to -8.00 D (0.50 D steps)
Lens Diameters:	14.2mm
Base Curve:	Each lens type has a single base curve. The base curve of the Invigor A lens is 8.5mm and the Invigor B is 8.6mm.

3.2 Lens Packaging and Labeling

Each lens blister pack is labeled with power, diameter, base curve, lot number, expiration date, quantity, lens name, sterility method/status and manufacturing location. The blister and outer packaging is identified as investigational product with the statement, "Caution-Investigational device, Limited by Federal (or US) law to Investigational use".

3.3 Lens Product Accountability

Test and Control lenses will be tracked through the use of base curve, power and lot numbers imprinted on the label. All lenses received by the investigational sites will be verified against the enclosed packing slip. All lenses dispensed to the study subjects during the investigation will be recorded on Inventory Control- Lens form. The site will be responsible for inventory management, limited access storage and continued inventory accountability. The study monitor will reconcile inventories remaining at the sites against product released to, received by the sites and used during the investigation. Procedures for the study product accountability are detailed in Section 5.8.

3.4 Indications for Use

Both Test and Control lenses are intended to be used as daily wear lenses for the correction of visual acuity in persons with non-diseased eyes with no more than 1.50 diopters of refractive astigmatism with a recommended replacement period of one month.

3.5 Subject Adjunct Products to be Used in the Study

The Test and Control lenses are designed for frequent replacement.

Johnson & Johnson Blink RevitaLens® Multipurpose Disinfecting Solution will be the primary multi-purpose lens care system for this study. Alcon Clear Care® Cleaning and Disinfection Solution will be used as an alternative for those subjects who have a history of, or present with, sensitivities or reduced wearing times associated with chemically preserved multi-purpose lens care systems. Subjects may be switched from Johnson & Johnson Blink RevitaLens® Multipurpose Disinfecting Solution to the Alcon Clear Care® Cleaning and Disinfection Solution, if required due to symptoms. Menicon LacriPure will be dispensed at the licensed investigators discretion to be used as a rinsing solution following disinfection with Alcon Clear Care® and prior to lens insertion. Minor solution related symptoms or subjective findings do not qualify as an adverse event unless accompanied by the presence of a grade 3 or greater slit lamp finding.

Investigational Sites will be provided with Eye-Cept, a non-preserved single dose rewetting drops containing an aqueous solution of sodium chloride and boric acid. Eye-Cept Rewetting Drops are the **only** rewetting drops that may be used by study subjects.

The use of over-the-counter (OTC) artificial tears while wearing lenses is prohibited in this study.

3.6 Occupational Hazards and Safe Handling

No specific occupational hazards have been identified with the use of contact lenses. Use of lenses in dry or dusty environments is discouraged. The use of lenses while swimming or soaking in hot tubs is prohibited during this study. **Handling of contact lenses should always be done with clean and dry hands.**

3.7 Storage Requirements and Expiration Dating

It is recommended that all lenses and solutions be stored at room temperature out of direct sunlight. They should not be allowed to freeze prior to use or during overnight storage as this may damage the lens material or solutions formulations. The product expiration date is printed on the immediate lens and solution packaging.

3.8 Dosage and Administration

Contact lenses are user applied devices. Only one study contact lens per eye at any one time is allowed.

3.9 Training for Use of the Study Products

The study subjects must be instructed and determined to be competent by the investigational site as to the proper handling, insertion and removal techniques, use and replacement of care systems and the proper accounting and disposal of the used lenses. Training will be in accordance with the information provided in Appendix H for each product. Patient care instructions will be provided to the subject at the time of initial lens dispensing.

3.10 Surgical and/or Medical Procedures

No specific surgical procedures are required as a part of this investigation. Standard ophthalmic examination procedures will be performed during the study visits.

4 JUSTIFICATION FOR THE STUDY

4.1 Literature Review

A review of the literature associated with hydrogel and silicone hydrogel contact lenses has indicated that the use of contact lenses is a safe and effective means of correcting visual acuity in persons with non-diseased eyes.

4.2 Summary of Preclinical Studies

Toxicological and microbiological testing as listed in the United States Food & Drug Administrations' (FDA) Premarket Notification 510(k) Guidance Document for Daily Wear Contact Lenses (May 1994) as well as the appropriate normative guidance documents found in ISO 14534 have been performed on the Test Lens material. The material has been found to be suitable for clinical studies based on the results of this testing. Summaries of these results have been provided to the IRB within the Investigator Brochure as part of the protocol review. This information will also be included for Investigator review within the Site Binder. The Control Lens is an FDA-cleared device; therefore, no additional preclinical studies have been performed on this lens prior to this clinical investigation.

4.3 Summary of Previous Clinical Studies

Please refer to the Investigator Brochure for a summary of the previous clinical investigations conducted for the lenses used in this study.

4.4 Potential Risks and Benefits for Human Subjects

4.4.1 This study is considered to be non-significant risk, based on the United States Food & Drug Administration and International Standards Organization guidelines when the use is daily wear with frequent replacement during the study. The risk to the subject is also reduced based on the results of toxicology testing and the history of similar devices currently approved and marketed.

4.4.2 The risks associated with contact lens wear have been established through device evaluations and market reporting. The risks may include discomfort, dryness, aching or itching eyes, excessive tearing, discharge, hyperemia and variable or blurred vision. More serious risks may include photophobia, iritis, corneal edema, corneal infiltrates and microbial keratitis.

4.4.3 The benefits of the Test Lens to the subjects are the possibility of improved vision, improved comfort and improved ocular health over other frequent replacement contact lenses due to the design and material characteristics of the lenses.

5 CLINICAL STUDY DESIGN

This study is a multi-center, randomized, licensed investigator and subject masked, concurrent control investigation that will enroll and screen up to one-hundred (100) subjects with the intention of successfully dispensing ninety (90) subjects for a study duration of approximately three months. Only subjects meeting the historical, refractive, ocular health and lens fitting and dispensing inclusion and exclusion criteria will be allowed to complete the dispensing visit. The study duration from dispensing to completion will be a minimum of 91 days.

The design of this clinical study is based on the United States FDA Premarket Notification (510(k)) Guidance Document for Daily Wear Contact Lenses May 1994 and the ISO 11980:2012(E) Ophthalmic optics – Contact lenses and contact lens care products – Guidance for clinical investigations.

5.1 Investigator/ Site Selection and Qualification

Up to six (6) investigational sites will be selected based on the experience of the site investigator(s) and staff in conducting clinical research trials, the availability of potential study subjects, and the availability and interest of the site in performing the trial.

All required and appropriate, documentation to meet the ISO 14155 and FDA GCP guidelines as well as [REDACTED] SOPs will be completed prior to the release of the investigational products to the site. If requested in writing, [REDACTED] will follow the Sponsor's SOPs for clinical study documentation.

At a minimum, a signed Site/Investigator Agreement, Financial Disclosure Document, Proof of Liability Insurance (Both Site and Sponsor Indemnification) Statement of Investigator Document, IRB approval letter, Delegation of Authority, Certification of Electronic Signature and Site Electronic Data Originators Authorization Log must be completed. Documents must be received by [REDACTED] the [REDACTED] Study Monitor prior to investigational material being released to the study site.

5.4.2 Efficacy Endpoints

The primary efficacy endpoint in this evaluation will be a comparison of the reported Snellen distance visual acuities as associated with the Test and Control lenses during scheduled visits. It is expected that the lens Snellen distance visual acuity results will be substantially equivalent between the Test and the Control lenses.

In addition, visual acuity with the Test and Control Lenses at the final study visit will be compared to the Test and Control Lens visual acuity at the Fitting visit. All changes ≥ 2 lines of visual acuity will be explained and compared across the Test and the Control lens groups. It is expected that the results will be substantially equivalent between the Test and the Control lens groups.

[REDACTED]

5.5 Methods and Timing for Assessing, Recording and Analyzing Data

The study design calls for a series of scheduled visits, bounded by specific observational windows, at which the study variables will be assessed using standard ophthalmic examination techniques, and recorded using electronic data capture. It is desirable to collect scheduled visit data with at least four (4) hours of lens wear at the time of scheduled follow-up visit.

Monitoring of the data will be routinely performed during the study while there are active subjects. Remote monitoring will be continuously performed to review the case report form data for individual subjects. Data analysis of the study variables will be performed following the completion of the study at a time when all subjects have exited the study. The study database must be cleaned, audited and locked prior to final analysis.

5.6 Equipment Used for Assessments

Each site must have the maintenance records (both preventive and equipment failure) and where appropriate the calibration records (**within the last 12 months**) for equipment used to perform standard ophthalmic examinations. This includes but is not limited to:

- Phoropter (manual or automatic) or trial lens frame and lenses.
- Snellen Visual Acuity Charts calibrated for the appropriate test distance.
**
- Keratometer (manual or automatic) – topography or corneal mapping equipment may be used for assessing keratometric measurements as long as the same instrument and function are used for all subjects at all visits.
**
- Lensometer: (manual or automatic) **

- Slit Lamp Biomicroscope or Videoscope
 - ** Calibrations records required to be maintained in Investigational Site files.

Grading scales for recording the observations are provided in Appendix E.

5.7 Investigational Lens and Comparator

This study has one investigational (Test) silicone hydrogel contact lens, and one FDA cleared comparator (Control) silicone hydrogel contact lens.

5.7.1 Investigational Test Lenses

The Test Lens is an investigational contact lens manufactured by CooperVision Inc.

5.7.2 Comparator Control Lenses

The Control Lens is a contact lens currently marketed and manufactured by CooperVision Inc. The Control Lens was chosen because it has been cleared by FDA for daily wear with a frequent replacement and has a known safety profile.

5.7.3 Exposure to Study Lenses

Study subjects are dispensed with either the Test or the Control lenses. The subjects will use the lenses for daily wear with frequent replacement schedule of one month. If needed, the licensed investigator may adjust the replacement schedule to a shorter replacement schedule to improve the wearing experience or ocular health of the subject. Reasons for prescribing a shorter replacement cycle will be documented on the comments section of the eCRFs. The subject's total exposure to the lenses will be based on each subject's reported daily lens wearing time, average days worn per week and length of time in the study.

5.7.4 Concomitant Medication/Treatment

No concomitant medications or treatments are planned for use in this study.

5.7.5 Anticipated Number of Study Lenses Used

It is anticipated that approximately 600 Test Lenses will be used by 60 subjects (120 eyes) and approximately 300 Control Lenses will be used by 30 subjects (60 eyes) during the three-month study period.

The number of lenses projected for use by both the Test and the Control subjects over the duration of the study (average 10 lenses per subject) is based on the fact that the lenses are intended to be discarded at the Month 1, Month 2 and Month 3 visits. Therefore, each subject successfully completing the study is expected to use a minimum of 3 lenses per eye, six (6) lenses in total, during the 3-month (91 Day) period. In addition, subjects may replace lenses for a variety of reasons during the study, raising the lens usage totals. Reasons for all lens replacements including scheduled replacements will be captured on the Lens Usage Cards. These cards will be issued to the study subjects as needed and reviewed by the study coordinator at each study follow-up visit.

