6.3.1 Scheduled Visit Windows

The week-1, week-2 and monthly follow up visits will have visit windows that are based on the time from the dispensing visit date as follows:

Table 1: Examination Visit Windows

Days from Dispensing (Day 0)		
	Earliest	Latest
Week 1	5	9
Week 2	12	16
Month 1	26	34
Month 2	56	64
Month 3	91	105

Scheduled visits will be the first visit within the visit window where the subject presents wearing lenses. Visit schedules will be calculated at the time of dispensing by the tablet software and available to the investigational site for scheduling follow-up visits.

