8 STATISTICAL CONSIDERATIONS

8.1 Study Design, and Analytical Method

The primary objective of this evaluation is to provide evidence supporting substantial equivalence for the primary safety and efficacy variables of the Test Lens compared to the currently cleared and marketed Control Lens when used in a daily wear modality with an anticipated replacement period of approximately 30 days wear.

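### Does the late Month 3 window leave lenses well past one month old at the final assessment?

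*Combined protocol and SAP*

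**What the plan says.** Section 2 sets the objective as equivalence "when used in a one month recommended replacement, daily wear modality", and section 3 describes "a daily wear schedule with a recommended replacement schedule of one month". Section 5.7.3 gives a "frequent replacement schedule of one month" and adds that "the licensed investigator may adjust the replacement schedule to a shorter replacement schedule"; it makes no provision for lengthening it. Section 8.1 speaks of an "anticipated replacement period of approximately 30 days wear".

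Section 5.7.5 is a supply projection. It says that "the lenses are intended to be discarded at the Month 1, Month 2 and Month 3 visits", derives from this a minimum of three lenses per eye, and budgets an average of ten lenses per subject because "subjects may replace lenses for a variety of reasons during the study". Subjects receive cards on which replacements, including scheduled ones, are noted.

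The visit dates stand in section 6.3.1, under "Table 1: Examination Visit Windows": Month 1 on days 26 to 34, Month 2 on days 56 to 64 and Month 3 on days 91 to 105, counted from dispensing as day 0.

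Two further sections bear on the point. Section 5.7.6 has sites assess adherence to the replacement frequency at each follow-up visit, with reinstruction and then exit if non-compliance persists. Section 5.8 requires used lenses of any age to be discarded at the exit visit and unused ones to be returned.

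**The concern.** Read literally, section 5.7.5 ties lens changes to the three monthly visits. The first two windows sit evenly around 30-day steps. The third does not: its earliest day is 91 and its midpoint 98. A subject who put on a third pair at Month 2 and kept it until Month 3 could be wearing lenses close to seven weeks old under a schedule that provides only for shortening.

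Month 3 is the final scheduled visit. For completers it supplies the acuity used in the comparison of changes of two lines or more (sections 5.4.2 and 8.5), and it is the last scheduled slit lamp examination. If lenses there are well past one month, the visit describes a longer replacement interval than the one claimed. If subjects instead change every 30 days, the Month 3 lens is nearly new. Either way, a reader could ask how well Month 3 represents one-month replacement.

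**Working it through.** **The plan's own figures.** From section 5.7.5: 60 × 10 = 600 Test lenses, 30 × 10 = 300 Control lenses, and 3 lenses × 2 eyes = 6 as the minimum per completer. All reproduce.

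**Lens age if changes happen only at visits** (windows from section 6.3.1). Minimum age = earliest day of the later visit − latest day of the earlier visit. Maximum age = latest day − earliest day.

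| Pair | Seen at | Minimum | Maximum | Midpoints |
|---|---|---|---|---|
| First | Month 1 | 26 − 0 = 26 | 34 − 0 = 34 | 30 − 0 = 30 |
| Second | Month 2 | 56 − 34 = 22 | 64 − 26 = 38 | 60 − 30 = 30 |
| Third | Month 3 | 91 − 64 = 27 | 105 − 56 = 49 | 98 − 60 = 38 |

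There are 9 × 15 = 135 permitted combinations of Month 2 and Month 3 dates. The third pair is older than 30 days in 125 of them, older than 31 in 120 and older than 35 in 90. These count permitted dates; they do not forecast attendance. With Month 3 on day 91, the basis of the lens count, the range is 91 − 64 = 27 to 91 − 56 = 35 days.

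**Lens age if changes happen every 30 days.** Changes fall on days 30, 60 and 90, so the Month 3 lens is 91 − 90 = 1 to 105 − 90 = 15 days old. A fourth lens per eye is then in use by day 91. That is 4 × 2 = 8 lenses per subject: above the stated minimum of 6, within the budgeted average of 10.

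**Days worn instead of calendar days.** Section 8.1 speaks of days of wear. Wear frequency during the study is not given, so I assume 5 to 7 days a week. Then 38 calendar days is 38 × 5/7 = 27 to 38 days worn, and 49 is 49 × 5/7 = 35 to 49. The midpoint case may not exceed 30 at all; the extreme case still does.

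**Does the premise hold?** Nothing visible says that lenses are changed only at visits. Subjects hold spare lenses (section 5.8 has them return the unused ones), the budget exceeds the minimum by 10 − 6 = 4 lenses per subject, and the replacement cards are issued to the subjects. The discard at Month 3 can equally be the end-of-study discard that section 5.8 requires, since completers exit after that visit (section 6.6).

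**Does it reach a result?** The windows are the same in both arms. Primary acuity uses the scheduled visits (section 8.5), and safety uses all scheduled and unscheduled follow-up visits (section 8.4). Section 8.2 sets no significance level or power that lens age could disturb.

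**The case for a change.** The strongest case for a change does not depend on when lenses are swapped. Three lenses per eye, each used for at most 31 calendar days, cover 3 × 31 = 93 days. A completer who uses only that minimum and attends Month 3 on any of days 94 to 105 (12 of the 15 permitted days) must have used at least one lens for longer than 31 days. Conversely, a 30-day calendar schedule needs a fourth lens, so the minimum of three fails. Section 5.7.6 adds a practical edge: sites judge adherence to replacement frequency and may exit subjects, yet the visible text does not say whether a lens of, say, 45 days discarded at Month 3 is compliant.

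The mismatch in wording stands. Its reach is short. The minimum of three is a floor in a supply estimate, quoted for a 91-day period, and the budget already exceeds it. The Month 3 window opens at day 91 because follow-up must last at least that long (sections 5 and 5.13); it says when a subject is examined and does not authorise longer wear. Sites might differ on borderline cases, but the licensed investigator, who may exit a non-compliant subject, is masked to the lens (section 5), so this gives no evident route to a difference between arms.

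**Conclusion.** No change to the plan follows. The ages are exact under their condition (27 to 49 calendar days, 38 at midpoints), but no visible text imposes the condition. The recommended and approximate wording, and a days-worn reading, absorb part of the excess. No bias between Test and Control is shown, no passage links lens age in this range to acuity or slit lamp findings, and neither primary comparison rests on Month 3 alone. The effect is on how Month 3 is described.

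An analyst who wants lens age at Month 3 can derive it from the replacement cards and from the Lens Replacement Form completed at scheduled visits (Table 2), provided that dates are recorded, which the visible text does not confirm. Section 8.7.5 already puts all data into tables or listings.

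Sections 5.7.3, 5.7.5 and 8.1 and the visit windows do fit together loosely. Reconciling them is an editorial matter, and which replacement rule is meant is for the sponsor to state. The training material in Appendix H and the patient care instructions (section 3.9) were not available and may already settle it. The conclusion assumes that they do not require changes only at visits.
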